4.1.1 Year 2 Extension

In the extension phase, all participants who are currently enrolled in the dose escalation or efficacy study will be invited to extend their participation for approximately 1 year from the time of re-consenting. After the results of the first year of the study are unblinded (approximately March 2023), children will be re-randomized 1:1 in a double-blind fashion within their original study arm assignment to receive either L9LS or placebo administered SC before the 2023 malaria season (Figure 3).

The protocol extension employs a pre-specified, adaptive design based on the time-to-event efficacy of 150 mg and 300 mg of L9LS observed after the first malaria season in the original protocol. Specifically, if 150 mg and 300 mg of L9LS both show ≥60% time-to-event efficacy against *P. falciparum* infection as detected by blood smear during the first malaria season (based on the upper bound of the two-sided 95% CI), children who received 150 mg of L9LS in year one will be randomized 1:1 in year 2 to receive either a second 150-mg dose of L9LS (arm 1a) or placebo (arm 1b); children who received 300 mg of L9LS in year one will be randomized in year 2 to receive either a second 300-mg dose of L9LS (arm 2a) or placebo (arm 2b); and children

Version Date: 14 March 2024

who received placebo in year 1 will be randomized in year 2 to receive either a first 150-mg dose of L9LS (arm 3a) or placebo (arm 3b) (Figure 3a).

If the 300-mg dose of L9LS shows ≥60% efficacy (based on the upper bound of the two-sided 95% CI) and the 150-mg dose of L9LS shows <60% efficacy (based on the upper bound of the two-sided 95% CI) but the difference between their respective point estimates of efficacy is ≤10%, children who received 150 mg of L9LS in year one will be randomized 1:1 in year 2 to receive either a second 150-mg dose of L9LS (arm 1a) or placebo (arm 1b); children who received 300 mg of L9LS in year one will be randomized in year 2 to receive either a second 300-mg dose of L9LS (arm 2a) or placebo (arm 2b); and children who received placebo in year 1 will be randomized in year 2 to receive either a first 300-mg dose of L9LS (arm 3a) or placebo (arm 3b) (Figure 3b). In the unlikely event that the 150-mg dose of L9LS shows ≥60% efficacy (based on the upper bound of the two-sided 95% CI) and the 300-mg dose of L9LS shows <60% efficacy (based on the upper bound of the two-sided 95% CI) but the difference between their respective point estimates of efficacy is ≤10%, the same design (Figure 3b) will be employed with the following exception: children who received placebo in year 1 will be randomized in year 2 to receive either a first 150-mg dose of L9LS (arm 3a) or placebo (arm 3b).

If the 300-mg dose of L9LS shows ≥60% efficacy (based on the upper bound of the two-sided 95% CI) and the 150-mg dose of L9LS shows <60% efficacy (based on the upper bound of the two-sided 95% CI) but the difference between their respective point estimates of efficacy is >10%, the 150 mg dose will be abandoned and children who received 150 mg of L9LS in year one will be randomized 1:1 in year 2 to receive either a 300-mg dose of L9LS (arm 1a) or placebo (arm 1b); children who received 300 mg of L9LS in year one will be randomized in year 2 to receive either a second 300-mg dose of L9LS (arm 2a) or placebo (arm 2b); and children who received placebo in year 1 will be randomized in year 2 to receive either a first 300-mg dose of L9LS (arm 3a) or placebo (arm 3b) (Figure 3c).

If 150 mg and 300 mg of L9LS both show <60% efficacy (based on the upper bound of the two-sided 95% CI) by time-to-event analysis after the first malaria season, the protocol extension will be abandoned.

Before study agent administration, all subjects will be given artemether-lumefantrine to clear any preexisting Pf blood-stage infection.

Subjects will be followed at study visits 1, 3, 7, 14, 21, and 28 days after administration, and once every 2 weeks thereafter through 28 weeks, with a final visit occurring on study day 252 (36 weeks) to collect a final PK sample. Primary study assessments include medical history, physical examination and blood collection for PK, ADA assessments, identification of Pf infection by microscopic examination of thick blood smears and RT-PCR, and other research laboratory evaluations.

Version Date: 14 March 2024

If 150 mg and 300 mg of L9LS both show \geq 60% efficacy during the first malaria season in the original protocol, the schema depicted in Figure 3a will be followed, and safety outcomes will be evaluated within arms to assess the safety of a second 150-mg dose of L9LS vs. placebo (1a vs. 1b); the safety of a second 300-mg dose of L9LS vs. placebo (2a vs. 2b), and the safety of a first 150-mg dose of L9LS vs. placebo (3a vs. 3b). In addition, safety outcomes will be evaluated between arms to assess the safety of a second 150-mg dose of L9LS vs. a first 150-mg dose of L9LS (1a vs. 3a). Finally, safety outcomes of L9LS vs. placebo will be evaluated in aggregate (1a + 2a + 3a vs. 1b + 2b + 3b).

PK of L9LS will be evaluated throughout the study at dose levels of 150 mg and 300 mg SC. The presence of ADA to L9LS will be assessed in sera of recipients at specific timepoints throughout the study and will be correlated with L9LS PK.

In exploratory analysis, L9LS serum concentration will be correlated with the risk of Pf infection (assessed by blood smear and RT-PCR) and clinical malaria. The protective efficacy of L9LS against *P. falciparum* infection (by blood smear and RT-PCR) and clinical malaria will be assessed by comparing the following arms:

- 1. Children who receive a second 150 mg dose of L9LS versus children who receive placebo (arms 1a vs. 1b).
- 2. Children who receive a second 300 mg dose of L9LS versus children who receive placebo (arm 2a vs. 2b).
- 3. Children who receive a second 150 mg dose of L9LS versus children who received placebo in years 1 and 2 (arms 1a vs. 3b).
- 4. Children who receive a second 300 mg dose of L9LS versus children who received placebo in years 1 and 2 (arms 2a vs. 3b).
- 5. Children who receive a first 150 mg dose of L9LS versus children who received placebo in years 1 and 2 (arms 3a vs. 3b).

The risk of 'rebound' malaria will be assessed in year two of the study by comparing the risk of clinical malaria in the following arms:

- 1. Children who received a 150 mg dose of L9LS in year 1 and placebo in year 2 versus children who received placebo in years 1 and 2 (arms 1b vs. 3b).
- 2. Children who received a 300 mg dose of L9LS in year 1 and placebo in year 2 versus children who received placebo in years 1 and 2 (arms 2b vs. 3b)

If 300 mg of L9LS shows \geq 60% efficacy (based on the upper bound of the two-sided 95% CI) and 150 mg of L9LS shows <60% efficacy (based on the upper bound of the two-sided 95% CI) but the difference between their respective point estimates of efficacy is \leq 10% during the first malaria season, the schema depicted in Figure 3b will be followed, and safety, PK, and efficacy

Version Date: 14 March 2024

outcomes will be conducted as described above, with the exception of Arm 3a that will evaluate children who received placebo in year 1 followed by 300 mg of L9LS in year 2.

If 300 mg of L9LS shows ≥60% efficacy (based on the upper bound of the two-sided 95% CI) and 150 mg of L9LS shows <60% efficacy (based on the upper bound of the two-sided 95% CI) but the difference between their respective point estimates of efficacy is >10% during the first malaria season, the schema depicted in Figure 3c will be followed, and safety, PK, and efficacy outcomes will be conducted as described above, with the exception of Arm 1a that will evaluate children who received 150 mg of L9LS in year 1 followed by 300 mg of L9LS in year 2.

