Arm 1: Up to 84 subjects who received 150 mg of L9LS in year 1 (9 from the dose-escalation study, plus 75 from the efficacy study).

Arm 2: Up to 84 subjects who received 300 mg of L9LS in year 1 (9 from the dose-escalation study, plus 75 from the efficacy study).

Arm 3: Up to 93 subjects who received placebo in year 1 (18 from the dose-escalation study, plus 75 from the efficacy study).

The protocol extension employs a pre-specified, adaptive design based on the time-to-event efficacy of 150 mg and 300 mg of L9LS against *P. falciparum* infection as detected by blood smear observed after the first malaria season in the original protocol. Specifically, if 150 mg and 300 mg of L9LS both show ≥60% efficacy during the first malaria season (based on the upper bound of the two-sided 95% confidence interval [CI]), participants will be re-randomized 1:1 in a double-blind fashion within each arm to receive a single dose of either L9LS (150 or 300 mg depending on study arm) or placebo administered SC before the 2023 malaria season.

The same randomization scheme will be followed if in the first malaria season the 300-mg dose of L9LS shows \geq 60% efficacy (based on the upper bound of the two-sided 95% CI) and the 150-mg dose of L9LS shows <60% efficacy (based on the upper bound of the two-sided 95% CI) but the difference between their respective point estimates of efficacy is \leq 10%, with the exception that children who received placebo in year 1 will receive 300 mg of L9LS (or placebo) in year 2.

If 300 mg of L9LS shows ≥60% efficacy (based on the upper bound of the two-sided 95% CI) and 150 mg of L9LS shows <60% efficacy (based on the upper bound of the two-sided 95% CI) but the difference between their respective point estimates of efficacy is >10% during the first malaria season, participants will be rerandomized 1:1 in a double-blind fashion within each arm to receive a single dose of either 300 mg of L9LS or placebo administered SC before the 2023 malaria season.

If 150 mg and 300 mg of L9LS both show <60% efficacy (based on the upper bound of the two-sided 95% CI) after the first malaria season, the protocol extension will be abandoned.

Before study agent administration, all subjects will be given artemether-lumefantrine to clear any preexisting Pf blood-stage infection.

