- 6. To explore the impact of pre-existing CSP antibodies on the protective efficacy and PK of L9LS.

- 1. Measurement of ADA to L9LS in sera of recipients.
- 2. Assessment of IgG1 allotypes and allotypes specific effects on L9LS PK.
- 3. Characterization of the cellular immune response to L9LS.
- 4. CSP genotyping of parasites isolated from study subjects.
- 5. Pre-existing parasitemia detected by microscopic examination of thick blood smears or RT-PCR before L9LS administration.
- 6. Pre-existing CSP-specific antibodies measured in sera collected before L9LS administration.

- ADA to L9LS may impact the PK and activity of L9LS.
- 2. Subject IgG1 allotype may impact the PK and activity of L9LS.
- 3. L9LS-induced cellular immune responses may be associated with Pf infection risk.
- 4. L9LS efficacy may be specific to certain Pf parasite genotypes at the CSP locus.
- 5. Pre-existing parasitemia may impact the protective efficacy and PK of L9LS.
- 6. Pre-existing
 CSP-specific antibodies
 may impact the
 protective efficacy and
 PK of L9LS.

Extension Phase Primary

Version Date: 14 March 2024

- 1. To evaluate the safety and tolerability of a second SC dose of L9LS administered at 150 mg and 300 mg (compared to placebo) in healthy Malian children.
- 2. To evaluate the PK of L9LS throughout the study at dose levels of 150 mg and 300 mg SC in healthy Malian children.
- 3. To determine if ADAs to L9LS can be detected in sera of recipients at specific timepoints throughout the study and to correlate the occurrence of ADAs with L9LS PK.

- 1. Incidence and severity of local and systemic AEs occurring within 7 days after the administration of L9LS.
- 2. Measurement of L9LS in sera of recipients.
- 3. Measurement of ADA in sera of recipients.
- 1. Assessment of AEs is a standard measure of study agent safety and tolerability.
- 2. Concentrations of L9LS in blood will help assess durability of L9LS at each dose level
- 3. ADA to L9LS may impact the PK and activity of L9LS.

Extension Phase Exploratory (see Figure 3 for study arm definitions)

- 1. To assess the efficacy of a second SC dose of L9LS at 150 mg and 300 mg (compared to placebo) in mediating protection against Pf infection and clinical malaria in healthy Malian children during a second malaria season (arms 1a vs. 1b; arms 2a vs. 2b), and to assess if this efficacy is influenced by whether or not a prior dose of L9LS was administered in year 1 (arms 1a vs. 3b; arms 2a vs. 3b).

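### Extension safety: there is no pooled contrast of second-dose children only, and in the main branch of schema b the one second-versus-first-dose contrast (1a vs 3a) mixes repetition with dose level

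*Combined protocol and SAP*

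**What the plan says.** Section 3 states extension primary objective 1 as: "To evaluate the safety and tolerability of a second SC dose of L9LS administered at 150 mg and 300 mg (compared to placebo". Under section 4.1.1, "children will be re-randomized 1:1 in a double-blind fashion within their original study arm assignment to receive either L9LS or placebo administered SC".

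For schema a, section 4.1.1 lists five safety contrasts:

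- second 150 mg dose against placebo: "safety outcomes will be evaluated within arms to assess the safety of a second 150-mg dose of L9LS vs. placebo (1a vs. 1b";
- second 300 mg dose against placebo: "the safety of a second 300-mg dose of L9LS vs. placebo (2a vs. 2b";
- first 150 mg dose against placebo, 3a vs 3b;
- second against first dose: "safety of a second 150-mg dose of L9LS vs. a first 150-mg dose of L9LS (1a vs. 3a";
- all L9LS against all placebo: "safety outcomes of L9LS vs. placebo will be evaluated in aggregate (1a + 2a + 3a vs. 1b + 2b + 3b".

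For schema b, the same section says that "outcomes will be conducted as described above, with the exception of Arm 3a that will evaluate children who received placebo in year 1". The year 2 dose of arm 3a in that branch is 300 mg, while arm 1a still receives a second 150 mg dose. Section 4.1.1 also describes a reversed variant of schema b, in which 150 mg meets the 60% criterion and 300 mg does not; arm 3a then receives 150 mg.

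For schema c, the analysis paragraph names only arm 1a as the exception. The design paragraph of section 4.1.1 and the footnote to Table 1 also move arm 3a to 300 mg.

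**The concern.** The extension exists largely to study repeat dosing. Section 2.2.3 gives the reason: anti-drug antibodies, particularly after repeated dosing, can promote local and systemic immune reactions. A child in arm 3a has had no earlier dose and cannot show a reaction that depends on one. Pooling 3a with 1a and 2a therefore shrinks the visible excess of such a reaction, and no listed contrast pools only the second-dose children.

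The contrast 1a vs 3a is the only one that asks whether a second dose behaves differently from a first. Read literally in the main branch of schema b, it compares two groups that differ in both dose number and dose level. An excess due to repetition could be offset by more reactions at the larger first dose. Equally, a dose effect could be taken for a repetition effect.

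**Working it through.** **Inputs.** The Synopsis gives the maximum numbers who could continue: "Up to 84 subjects who received 150 mg of L9LS in year 1", 84 who received 300 mg and 93 who received placebo. Table 1 gives 42 in each of 1a, 1b, 2a and 2b, and 46 in each of 3a and 3b. Section 9.5.1.1 sets two-sided 0.05 with no multiplicity adjustment. The adverse event rates in steps 3 and 4 are assumptions; the protocol gives none for a first or second dose.

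**1. The plan's own figures.** Section 9.3 claims 90% power with 42 per arm for 0.01 vs 0.24, 0.05 vs 0.33 and 0.10 vs 0.42. Exact power of Fisher's test by enumeration is 90.2%, 90.9% and 91.0%, so the claim reproduces. The Table 6 intervals reproduce as Clopper-Pearson intervals, including the upper bound of 0.084 for zero events in 42.

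**2. First-dose share of the aggregate.** n(3a)/[n(1a)+n(2a)+n(3a)] = 46/(42+42+46) = 46/130 = 35.4%. If 3a has the one extra child that the Figure 3 legend allows, it is 47/131 = 35.9%. Both use maximum sizes, so the share will move with continuation in each arm.

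**3. Dilution and power.** Assume 20% after a second dose and 5% on placebo, and let f be the first-dose rate. The aggregate L9LS rate is (84 × 0.20 + 46 × f)/130. At f = 0.05 it is (16.8 + 2.3)/130 = 14.7%, so an excess of 15 points appears as 9.7 points, which is 84/130 = 65% of it.

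Exact Fisher power, two-sided 0.05, ignoring stratification:

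| Contrast | First-dose rate f | L9LS rate | Power |
|---|---|---|---|
| One dose level, 42 vs 42 | not involved | 20% | 44% |
| Second-dose pool, 84 vs 84 | not involved | 20% | 82% |
| Aggregate, 130 vs 130 | 5% | 14.7% | 70% |
| Aggregate | 8% | 15.8% | 78% |
| Aggregate | 10% | 16.5% | 82% |
| Aggregate | 12% | 17.2% | 86% |
| Aggregate | 15% | 18.2% | 90% |

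The two pooled contrasts cross at a first-dose rate of about 10%.

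**4. Zero-event bound.** The upper 95% limit is 1 − 0.025^(1/n): 8.4% for n = 42 and 4.3% for n = 84.

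**5. What 1a vs 3a compares in each branch (year 2 doses).**

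| Branch | 1a | 3a | 2a | Reading |
|---|---|---|---|---|
| Schema a | second dose, 150 mg | first dose, 150 mg | second dose, 300 mg | 1a vs 3a dose-matched |
| Schema b, main | second dose, 150 mg | first dose, 300 mg | second dose, 300 mg | 1a vs 3a mixes repetition and dose; 2a vs 3a is matched but not listed |
| Schema b, reversed | second dose, 150 mg | first dose, 150 mg | second dose, 300 mg | 1a vs 3a dose-matched |
| Schema c | 300 mg after 150 mg | first dose, 300 mg | second dose, 300 mg | 1a vs 3a matched on year 2 dose; 2a vs 3a (second vs first 300 mg) not listed |

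**The case against.** The strongest reply is that the primary objective is already met. It asks about a second dose at each level against placebo, and 1a vs 1b and 2a vs 2b do exactly that: they are randomised within Year 1 arm and contain no first-dose children, and schema b changes neither. The second-versus-first comparison is additional and is not part of the objective. The aggregate is described as L9LS against placebo, and including 3a is right for that question. All of this stands. A reader might infer that the planned contrasts fail to isolate a second dose, or that the primary safety objective could be answered wrongly; section 4.1.1 supports neither.

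A second reply is that the dilution argument depends on a first dose causing no excess. Section 2.3.1 expects local and systemic reactions to monoclonal antibodies generally, so that is the case least favourable to the aggregate. This also stands: the table shows the pool's advantage gone at a first-dose rate of about 10%.

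Third, 1a vs 3a was written as a comparison at equal dose, and the schema b text openly says that 3a changes. It is fair to read this as an unfinished carry-over, not an intention to compare unlike doses. The text still does not say what replaces 1a vs 3a.

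Finally, this version is dated 14 March 2024, and the branch was to be chosen after unblinding in about March/April 2023. The documents do not say which schema applied, so the schema b point may be moot.

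**Conclusion.** The point holds in limited form. Second-dose safety against placebo is validly estimated at each dose level, but with 42 per arm, where 90% power needs a contrast as large as 5% vs 33%. The one pooled contrast carries up to 35% first-dose children and shows about 65% of an excess that occurs only on re-exposure. A second-dose pool would raise power from 44% to 82% under the assumed 20% and 5% rates, and would lower the zero-event upper bound from 8.4% to 4.3%. It outperforms the aggregate only while the first-dose rate is below about 10%. That justifies adding the pool; it does not show the aggregate to be wrong.

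In the main branch of schema b, the only listed second-versus-first contrast is confounded with a two-fold dose difference, and the matched contrast is missing. This does not extend to schema a or to the reversed variant of schema b. The schema c wording is incomplete because it omits the change to arm 3a.

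The figures rest on the maximum arm sizes and on illustrative event rates.

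**What to change.** In section 4.1.1, change the analysis wording only:

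- **Schema b, main branch:** replace 1a vs 3a with 2a vs 3a, second against first 300 mg dose. Keep 1a vs 3a for schema a and for the reversed variant.
- **Schema c:** list 2a vs 3a as well. Reconcile the analysis paragraph, which names only arm 1a as the exception, with the design paragraph and the Table 1 footnote, where 3a also changes.
- **All schemas:** add 1a+2a vs 1b+2b, stratified by Year 1 arm, beside the per-dose contrasts and the existing aggregate. State that it targets re-exposure and that the aggregate targets L9LS against placebo overall.

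The cost is one or two extra tables from data already collected, with no change to conduct. The drawback is that the pool averages over dose levels (150 and 300 mg in schemas a and b), so it supplements the per-dose contrasts that the objective names and cannot replace them. If the branch is already known, only the text for that branch and the added pool are needed.

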4.2 Scientific Rationale for Study Design

This two-part study was designed to test L9LS in the setting of naturally occurring Pf infection and in a population that could potentially benefit from a novel therapeutic for malaria prevention, with initial safety data collected from adults prior to proceeding with the enrollment of children.

Both parts of the study will use randomization and a double-blind design in the cohorts of children to minimize bias in subject selection and study assessments. The placebo will be inactive (normal saline) rather than a comparator MAb, as currently there are no licensed antimalaria MAbs available.

4.2.1 Year 2 Extension

The protocol extension was designed to evaluate the safety and PK of a second dose of L9LS in the setting of naturally occurring Pf infection and in a population that could potentially benefit from a novel therapeutic for malaria prevention.

As with the original protocol, the protocol extension will use randomization and a double-blind design in the cohorts of children to minimize bias in subject selection and study assessments. The placebo will be inactive (normal saline) rather than a comparator MAb, as currently there are no licensed anti-malaria MAbs available.

4.3 Justification for Dose

The doses used in this study were selected based on preclinical data and data generated in the ongoing phase 1 VRC study, which tested the dose range included in this protocol. This study will test fixed doses of L9LS in children in a defined range of subject weights to approximate the weight-based dosing used in the phase 1 VRC study. Compared to weight-based dosing, fixed dosing will provide a greater range of antibody concentrations in vivo for determining a protective L9LS titer. Fixed dosing is also simpler to administer, reduces the risk of medication errors, and is generally more cost effective—factors that are relevant to the potential use of L9LS in malaria-endemic regions.

Version Date: 14 March 2024

In the safety study, subjects aged ≥18 years weighing 60 kg or less will receive a SC dose of 300 mg (2 mL) or 600 mg (4 mL), approximating the weight-based dosing of 5 mg/kg and 10 mg/kg, respectively, in a 60-kg adult. An additional group of subjects aged ≥18 years weighing 60 kg or less in the safety study will receive an IV dose of 20 mg/kg. This dose will be administered IV rather than SC because 4 mL is the maximum volume of L9LS that will be administered SC in this study. In Kalifabougou, the average weight of adult females and males is 55.6 kg and 61.7 kg, respectively. In the safety and efficacy studies, subjects aged 6-10 years weighing ≥15 kg and ≤30 kg will receive a dose of 150 mg or 300 mg SC, approximating the weight-based dosing of 5 mg/kg and 10 mg/kg, respectively, in a 30-kg child, and 10 mg/kg and 20 mg/kg, respectively, in a 15-kg child. Based on recent data from the study site, approximately 85% of children aged 6-10 years in Kalifabougou weigh between 15 kg and 30 kg. The doses used in the efficacy study will complement the data generated in the ongoing phase 1 VRC study. The doses used in the phase 1 VRC study were derived from 1) efficacy data from the challenge studies performed in mice showing that the protective concentration of antibody in vivo is between 5-100 µg/mL in 2 different mouse models of malaria infection; 11 and 2) PK data from nonhuman primate studies with L9LS and prior clinical experience in healthy adults with human MAbs targeting HIV (i.e., VRC01, VRC01LS, and VRC07-523LS) and ebolavirus (MAb114) at the same dose.

